#### 3.0 STATISTICAL METHODS

#### 3.1 Statistical Handling Policy

#### 3.1.1 Interim Safety Review

No formal interim analysis will be conducted, but a Medical Monitor will periodically do safety review of subject's adverse events data. If any safety concern should be identified, the Sponsor, institutional review board (IRB), and regulatory agencies, if applicable, will be informed immediately.

## 3.1.2 Analysis of 1-Year data

An analysis of the 1-year data was performed after all the subjects are enrolled and all the 1-year data were collected, monitored, and cleaned. All outputs in Section 5.2 that involve 1-year data were created since this analysis was the final analysis of the 1-year data. The analysis of 1-year data was the main analysis for the study. Secondarily, an analysis will be done at the end of the study to include all 3-year data.

## 3.1.3 Analysis Conventions

This section details general policies to be used for the statistical analyses. Departures from these general policies may be given in the specific detailed sections of this statistical analysis plan. When this situation occurs, the rules set forth in the specific section take precedence over the general policies. The following policies will be applied to all data presentations and analyses.

- Summary statistics will consist of the number and percentage of responses in each category for discrete (categorical) variables, and the number of non-missing observations (n), mean, median, standard deviation (SD), minimum, and maximum (abbreviated as 6-number summary statistics) for continuous variables.
- All mean values will be formatted to one more decimal places than the measured value, and standard deviation values will be formatted to two more decimal places than the measured value. For median values, they will be kept the same decimal place as the measured values if that is doable without losing accuracy; otherwise, they will be formatted to one more decimal place than the measured values.
- All percentages will be rounded to one decimal place. The number and percentage
  of categorical responses will be presented in the form XX (XX.X), where the
  percentage is in the parentheses. The denominator for percentage calculations will
  be either the number of non-missing observations (n) when this number is shown, or
  the total sample size of the relevant sample size for tables of adverse events, medical
  histories, or other tables where this number of non-missing observations (n) is not
  presented.
- All listings will be sorted for presentation in the order of site identifier, subject identifier, and date of procedure or event.
- When necessary for analysis purposes, partial dates will be completed (i.e., turned into complete dates) using the most conservative approach.
- All analysis and summary tables will have the population sample size in the column heading.
- Baseline is defined as the last data point before the placement of study product.
- Calculating change from baseline to a visit will be done as follows: Change from Baseline = Observed value at the visit – Baseline value.
- Subjects who have only baseline (without any post-baseline measurements) for a
  parameter at a visit, or only have post-baseline value for a parameter at a visit, will be
  excluded from the summary of change from baseline by visit for that parameter.

• Version 9.4 of SAS® or higher will be the statistical software package used to produce all summaries, listings, statistical analyses, and graphs.

## 3.2 Subject Disposition

Subject disposition will be summarized for the All Screened population with the following data:

- Total number of subjects who consented, enrolled and screen failures.
- The number and percentage of subjects who completed or discontinued prematurely
  from the study, either prior to the end of 1-year study or prior to extension study; the
  number and percentage of subjects who discontinued and reason for discontinuation,
  either 1-year or extension study, by each reason for all subjects. For those entered
  Extension, similar summaries will be presented for 2-year and 3-year benchmark.
- A listing of subjects who discontinued prematurely from the study, either 1-year or extension. The listing will include information about study site ID number, subject ID number, age, subject is parous or nulliparous, number of days on study, and reason for discontinuation. The number of days on study will be calculated as Device Removal Date – Device Placement Date + 1.
- The number and percentage of subjects at each scheduled visit.
- The number of subjects who were enrolled at each study site, the number and percentage of subjects who completed or discontinued either 1-year or extension, at each study site.

The End of Trial CRF will be used to determine who discontinued prematurely from the study.

#### 3.3 Protocol Deviations

Protocol deviations will be summarized by type of deviations listed on the CRF for all ITT subjects. Both the number of deviation events and distinct number and percentage of subjects will be presented for each type of deviation.

## 3.4 Analysis Populations

All Screened: all subjects who signed Consent Form and screened at the study sites.

Intent To Treat (ITT): All subjects who underwent the study device placement procedure, regardless of whether the study device was successfully placed or not.

Safety: ITT subjects who had the device successfully placed.

Extension: ITT subjects who agreed to continue study device use after 12 months, up to 2 additional years for a total maximum of 3 years.

Evaluable for Pregnancy (EP): ITT subjects who had VeraCept placed successfully, and must meet both requirements 1 and 2 to be EP. Subjects must also meet either requirement 3 or requirement 4 to be EP.

1. between 18 to 35 years of age (inclusive) at enrollment

2. at least one report of pregnancy status after being enrolled

AND

3. have at least 1 cycle of diary with intercourse and without any backup contraception or emergency contraception (EC)

OR

4. have an on-treatment pregnancy, which is defined as the estimated conception date being on or after the insertion date and no more than 7 days after the VeraCept is removed or expelled.

Evaluable for Cycle Control (ECYC): ITT subjects with at least one cycle for which:

- A) a pregnancy did not occur; AND
- B) there was an assessment of bleeding in the diary data; AND
- C) the cycle has 14 or more days data.

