10. ENROLLMENT

A subject is considered enrolled into the study after signing the informed consent, PHI and Bill of Rights forms and being found eligible based on her history, physical examination and screening tests. If an eligible consented patient withdraws consent before insertion for any reason this would be considered a screen failure.

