12.2 Visit 2: VeraCept Placement (Day 1)

VeraCept can be placed on any day of the menstrual cycle. Subjects must have a negative urine pregnancy test just prior to VeraCept placement. Initiation of the VeraCept is consistent with standard IUD placement. Refer to the Prescribing Information for specific instructions.

If placement is unsuccessful, a second attempt may be made within one (1) week following the first attempt. If a second attempt is also unsuccessful, the subject will be discontinued early from the study. The need for cervical dilation to facilitate placement of VeraCept will be left to the discretion of the investigator and subject; however, it is recommended that placement be tried first without prior cervical dilation. Use of cervical dilation will be recorded on the case report form. The need for pain control will also be left to the discretion of the investigator and subject. Any medications given for pain control will be recorded on the Concomitant Medications case report form.

Prior to VeraCept placement, the following evaluations will be completed:

- Entry criteria confirmed
- Vital signs and weight
- Physical Exam
- Pelvic Exam
- Pregnancy test, urine
- Prior and concurrent medications
- Any adverse events.

Following VeraCept placement, evaluations will be made for:

- VeraCept placement ease
- VeraCept placement pain
- VeraCept position (evaluated by Transvaginal Ultrasound)
- Concomitant contraception
- Need for contraception if VeraCept was not properly placed

Study site staff will review the completed diaries and discuss with the subject any further training that is required and answer any questions the subject may have about how to correctly complete the diaries.

New diaries will be dispensed to the subject at this time, along with instructions for proper completion of the diaries.

12.3 Visits 3-6 (Week 6±2,13±2, 26±2 and 52±2/ Exit after VeraCept placement to week 52)

The subject will return for follow up visits at preplanned intervals following placement of the VeraCept. At these follow up visits, the subject will be evaluated for:

- Vital signs and weight
- General physical exam (same as at Screening Visit)
- Pelvic exam (string check)
- Pregnancy test, urine
- Interval and concurrent medications
- Adverse events
- Diary collection and review with subject
 - Verify sexual activity and any back-up method is documented

Diary dispensing

Additionally, at the Week 52 / Exit visit, the following will also be performed:

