## 3.5.1 Demographics

The summary of demographics and subject characteristics will include age, race, ethnicity, education level, marital status, relationship status, how long the subject has been in her relationship, height, weight and body mass index (BMI) at baseline (from vital signs CRF), as well as uterine length (from pelvic exam CRF). The summary will be done for ITT, EP, ECYC, and include:

- The 6-number summary statistics (number of non-missing observations, mean, median, SD, minimum, and maximum) for age, height, baseline weight, baseline body mass index (BMI), and uterine length. Age will be calculated (with the INTCK function in SAS®) using the Screening Visit Date and the Date of Birth. Weight at baseline will be used for the summary.
- The number and percentage of subjects for categorical data, such as race, ethnicity, education level, parity (parous (≥1 birth) and nulliparous (not given birth)) marital status, relationship status, time (duration) of relationship, as well as the category of BMI: Underweight (< 18.5), Normal (18.5 24.9), Overweight (25.0 29.9), and Obese (≥ 30.0).

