## 3.7 Efficacy Analyses

## 3.7.1 Efficacy Analyses for Year 1 Data

Primary efficacy analysis was performed for the first year of the study (through Day 364) for Evaluable for Pregnancy population, by using Pearl Index. Pearl Index is defined as the number of pregnancies in 100 woman-years of method use. Pearl Index was calculated in subjects aged 18-35 at the time of VeraCept placement through the date of VeraCept removal or pregnancy, excluding the following cycles, unless the subject became pregnant in that cycle:

- When back-up contraception use was documented on the daily diary
- When the subject had no intercourse.

The Pearl Index formula is:

$$r = \frac{n}{L} \times 1300 = \frac{\text{Number of pregnancies}}{\text{Number of woman-cycles of pregnancy-risk}} \times 1300$$

where n is the number of pregnancies, and L is the number of woman-cycles, i.e., sum of the number of cycles each woman used the VeraCept up to and including the cycle of conception or until the time of VeraCept removal/expulsion, whichever comes earlier. The cycles of pregnancy-risk will be calculated as (Date of VeraCept removal/expulsion – Date of VeraCept placement + 1) / 28 for women who are not pregnant, and as (Date of pregnancy – Date of VeraCept placement + 1) / 28 for women who became pregnant

during the study. On-treatment pregnancies are defined to be pregnancies for which the estimated date of conception was within 7 days after study device expulsion or removal (the earlier of expulsion and removal dates will be used). The last cycle of pregnancy-risk can be a partial cycle and the partial cycle at risk is determined by dividing the number of days at risk in the cycle by 28 (e.g., 14/28 = 0.5 cycle of risk). If a cycle has a day with no information about backup contraception, that cycle will be excluded from the analysis (unless the subject became pregnant in that cycle).

To get the confidence interval (CI) for the Pearl Index, first the CI for the n (number of pregnancies) will be approximated by Poisson distribution sample mean's CI as

$$(\frac{\chi^{2}(\alpha/2;2n)}{2},\frac{\chi^{2}(1-\alpha/2;2n+2)}{2})$$

where  $\chi^2(\alpha/2;2n)$  in the lower limit is the Chi-square distribution (degrees of freedom = 2n) percentile with lower tail area (probability)  $\alpha/2$ , and  $\chi^2(1-\alpha/2;2n+2)$  in the upper limit is similarly defined. If n = 0, the lower limit will be set as 0.

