## 3.7.2 Efficacy Analyses for the Whole Study

Post-Year 1 sexual activity and contraceptive use information can be found in the Cycle Contact CRF, which was added since the Extension study (Year 2) started, i.e., this CRF wasn't present from the beginning of the study, but added as a mid-study change. Each record in this form is for one cycle and has the following 2 key questions for determining if a cycle is pregnancy-risk or not:

- Did the subject have intercourse at least once during the cycle? (Yes, No)
- Did the subject use backup contraception during the cycle? (Yes, No)

If the answer is "Yes" to the first question and "No" to the second question, or the subject was pregnant within a cycle (determined form the Pregnancy Test form), that cycle will be considered as a pregnancy-risk cycle; otherwise, the cycle will not be considered as a pregnancy-risk cycle.

For cycles without any Cycle Contact information, e.g., neither of the above 2 "Yes"/"No" questions were answered and a subject wasn't pregnant within the cycle either, the following procedure will be used to do the estimate for the subject:

- A. find the total number of such type of cycles for that subject
- B. find proportion of pregnancy-risk cycles from Year 1 diary data of the subject, which will be calculated as the number of pregnancy-risk cycles divided by the total number of cycles from Diary CRF
- C. The number from Step A is multiplied by the number from Step B, and then rounded to 1 decimal place, which will be the estimated number of pregnancy-risk cycles where Cycle Contact information is missing for the subject.

The number from Step C will be added to the number of pregnancy-risk cycles from those without missing Cycle Contact information, and then added to the Year 1 pregnancy-risk cycles from Diary CRF data to get denominator value of the Pearl Index for Year 2 (data cut off at 26 cycles) and Year 3 (data cut off at 39 cycles). The numerator will be the number of on-treatment pregnancies by the end of Cycle 26 and Cycle 39, respectively.

The Year 2 and Year 3 analyses will also be performed without inclusion of cycles with missing Cycle Contact information, i.e., not doing estimates of pregnancy-risk through the above Steps A, B, and C.

The 95% Confidence Intervals for the Pearl Index will be calculated, by using the formula in the above Section 3.7.1, at the following 3 scenarios:

- All EP subjects
- EP subjects with at least one live birth

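### EP entry for the 2- and 3-year Pearl Index rests on Year 1 diaries, so a woman without a qualifying diary cycle counts only if she conceives

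*SAP*

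**What the plan says.** SAP 3.4 builds EP from women with a successfully placed device who meet requirements 1 and 2 and either 3 or 4.

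- Requirement 1: age 18 to 35 at enrolment.
- Requirement 2: "at least one report of pregnancy status after being enrolled".
- Requirement 3: "have at least 1 cycle of diary with intercourse and without any backup contraception or emergency contraception (EC").
- Requirement 4: "have an on-treatment pregnancy, which is defined as the estimated conception date being on or after the insertion date" and no later than 7 days after removal or expulsion.

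The schedule (Protocol Table 1, repeated in SAP 5.1) dispenses diaries only up to Visit 5 and collects the last at Week 52. The long-term columns have none. For the extension, SAP 3.7.2 says: "Post-Year 1 sexual activity and contraceptive use information can be found in the Cycle Contact CRF". That form was added mid-study. A cycle is at risk if intercourse was reported and backup was not, or if the woman conceived in it. SAP 5.2 lists EP as the population for the 1-, 2- and 3-year Pearl Index tables and for the three Kaplan-Meier figures.

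On enrolment, Protocol 10 says: "A subject is considered enrolled into the study after signing the informed consent, PHI and Bill of Rights forms and being found eligible". Protocol 12.2 adds: "Subjects must have a negative urine pregnancy test just prior to VeraCept placement".

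On age, SAP 3.5.1 computes it with the SAS INTCK function "using the Screening Visit Date and the Date of Birth", while SAP 3.7.1 says: "Pearl Index was calculated in subjects aged 18-35 at the time of VeraCept placement".

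**The concern.** For a woman who does not conceive, the only way into EP is a Year 1 diary cycle. In the extension, however, risk is recorded on another form. If she has no qualifying diary cycle, her extension cycles are left out even when Cycle Contact shows them to be at risk under the SAP's own definition. If she conceives, requirement 4 brings her in. The numerator is then complete while matching pregnancy-free exposure is missing, and whether a woman enters the denominator depends on her outcome.

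The 2- and 3-year Pearl Index tables are at stake. The 24- and 36-month Kaplan-Meier figures use the same population.

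Two smaller looseness problems sit in the same definition. Requirement 2 is tied to enrolment rather than to placement, and three different dates are used for age.

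**Working it through.** **1. Entry rule against source of risk data**

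| Period | Route into EP without a pregnancy | Source of risk cycles |
|---|---|---|
| Year 1 (cycles 1-13) | Year 1 diary cycle | Diary |
| Years 2-3 (cycles 14-39) | Year 1 diary cycle | Cycle Contact CRF |

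In Year 1 the two agree: a woman with no qualifying diary cycle has no Year 1 risk cycles to add. The mismatch exists only in the second row.

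**2. Direction.** Take two women with no qualifying diary cycle and 26 at-risk extension cycles each (cycles 14-39), one of whom conceives in cycle 39. As written, the first enters with 1 pregnancy and 26 cycles and the second contributes nothing: 1/26 × 1300 = 50. Counting all observed risk gives 1/52 × 1300 = 25. The figures only illustrate that the rule can push the index up and not down.

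**3. The plan's own figures.** The inputs are in the protocol's sample size text: 225 women aged 18-35, 10 cycles each, 1% without diary data, 9.2% of cycles not at risk.

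- 225 × 10 × 0.99 × 0.908 = 2,022.6. With 222 whole women, 222 × 10 × 0.908 = 2,015.8. The plan states 2,015.
- Pearl Index with 1 pregnancy: 1/2,015 × 1300 = 0.645, stated as 0.6.

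**4. Size.** The documents do not say how many women are affected. As an assumption, take the 1% without any diary data: 225 × 0.01 = 2.25, about 2 women.

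- Most cycles each can lose: 26 − 13 = 13 by Year 2 and 39 − 13 = 26 by Year 3.
- Two women: 26 cycles by Year 2, 52 by Year 3.
- If D cycles are dropped from a full denominator of L + D, the index is inflated by the factor 1 + D/L. SAP 3.7.2 adds extension cycles to the Year 1 cycles, so L is at least 2,015 if Year 1 goes as planned.
- Largest inflation: 26/2,015 = 1.3% by Year 2 and 52/2,015 = 2.6% by Year 3. With 1 pregnancy and no other extension exposure, 0.645 would otherwise be 1300/2,041 = 0.637 or 1300/2,067 = 0.629.
- Range: none if no such woman exists; each further woman adds at most 13/2,015 = 0.65% (Year 2) or 26/2,015 = 1.3% (Year 3).

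**5. Missing Cycle Contact cycles.** SAP 3.7.2 Step B multiplies a woman's missing cycles by her Year 1 diary proportion of risk cycles. For the women at issue this is 0/k = 0 if k diary cycles exist and none qualifies, or 0/0 if no diary exists. The estimate cannot serve them.

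**6. Requirement 2.** Protocol 10 treats withdrawal before insertion as possible in an eligible, consented woman, so enrolment can precede placement. The Visit 2 urine test also precedes placement and can therefore satisfy requirement 2 with no status known after it.

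**7. Age.** Requirement 1 uses enrolment, SAP 3.5.1 uses the screening visit and SAP 3.7.1 uses placement. These can be different days, and the 35/36 boundary decides EP membership.

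**The case against.** The best defence is that little is touched. The 2- and 3-year tables are secondary. An affected woman must keep the device for a year without one qualifying diary cycle, although she enrolled expecting monthly intercourse and accepting the device as sole contraception. Requirement 3 matches Protocol 20.1. Keeping pregnancies is the plan's stated convention, and the bias runs against the device.

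Most of this stands and limits the size. The convention, however, keeps a pregnancy cycle that would otherwise be excluded. It does not call for dropping extension cycles that meet the SAP's definition of risk. Rarity is also not assured: SAP 3.7.1 excludes a cycle with one day lacking backup information. If requirement 3 is applied the same way, which SAP 3.4 does not say, a patchy diary could leave no qualifying cycle.

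On requirement 2, the schedule allows screening and enrolment visits to be combined, and entry criteria are confirmed again at Visit 2, so the test might be part of becoming enrolled. A reader might infer that the loose wording credits material exposure without known status. The documents do not support that: requirement 3 or 4 must still be met, pre-placement diaries are not analysed, and urine tests are scheduled at each of Visits 3 to 6, when diaries are collected.

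On age, a reader might infer that INTCK counts calendar years and so drops 35-year-olds from EP. The SAP names INTCK only under demographics, gives no interval or method, and does not say that this age decides EP. Combined visits may also make the dates coincide. What stands is the conflict of reference dates.

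**Conclusion.** The mismatch holds for the 2- and 3-year Pearl Index: non-pregnant women enter by a form that ends at Week 52, while extension risk is recorded on another. Entry then depends on the outcome and the index is biased upward.

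The primary Year 1 index is not affected, and it would be wrong to read this point as casting doubt on it. The effect is probably small. The ceilings in the working rest on three assumptions: about 2 affected women, every extension cycle at risk, and at least 2,015 Year 1 cycles. The true number of women cannot be derived from the documents.

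The wording of requirement 2 and the three age dates are minor. Loss of 35-year-olds is only a possibility to check in the program, and no size is attached to it because it would rest on two things the SAP does not state.

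**What to change.** For the 2- and 3-year analyses, reword requirement 3 to: *at least one pregnancy-risk cycle by Diary or Cycle Contact CRF*. For women admitted by Cycle Contact alone, count observed at-risk cycles only and apply no Step A-C estimate. Record the change as a departure from Protocol 20.1.

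Minor alignments:

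- Change requirement 2 to a report of pregnancy status *after VeraCept placement*.
- Use completed years at the placement date for both EP and the Pearl Index, and state how age is computed.

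The cost is a few phrases and one re-derivation of the EP flag, with no new data. SAP 1.0 says the final Year 2 and Year 3 analysis had not begun, so the rule can be set before it is run. SAP 3.1.2 records the 1-year analysis as completed and as the main analysis. Report any change in Year 1 EP membership as a check beside it, without replacing it.

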## 3.8.4 Device Expel and Subject Discomfort

All enrolled subjects will record device expel and discomfort through a daily diary:

- Experienced any unusual abnormal pain or pelvic pain or cramping? (None, Cramping Only, Pelvic Pain Only, Both Cramping and Pelvic Pain)
- Rate the discomfort (None, Mild, Moderate, Severe)
- Did the VeraCept device expel? (No, Yes, Suspected)

For each category of the question's answer (e.g., "Pain", Cramping", etc., all but "None" and "No"), the total number of days with that answer will be tabulated by cycle for each subject. If a cycle has less than 28 days but at least 14 days data, missing value will be imputed by the average in the same cycle for the subject, and then rounded to nearest integer.

For example, a subject at Cycle 6 has only 20 days data, of which 3 days with "Cramping". Then the total number of "Cramping" days at this cycle for her will be estimated as:

$$3 + (3 / 20 \times (28 - 20)),$$

which will be 4 after rounding to integer.

The six-number summary statistics will be presented by cycle for each parameter (i.e., categorical answer, all but "None" and "No"). Cumulative VeraCept device expulsion rates (%) at 1-year, 2-year, and 3-year will also be presented, which will be calculated as:

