# Subjects with device expulsion / # Subjects still in the study by that time-point x 100.

## 3.8.5 Bleeding and Spotting

Vaginal bleeding and spotting will be recorded daily by subjects in daily diary. The total number of bleeding or spotting days for each subject at each cycle, including the missing value imputation at cycles with less than 28 days but at least 14 days data, will be calculated similarly as the above Section 3.8.4, and then summarized by 6-number statistics for ECYC population. In addition, bleeding and spotting will be summarized separately. Subjects who discontinue the study due to bleeding complaints prior to completing one 28-day cycle will be included in the bleeding analysis.

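### For women who stop for bleeding with fewer than 14 diary days, the SAP's cycle-control population excludes them while its bleeding section says they are included, and no counting rule exists for them

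*SAP*

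**What the plan says.** SAP 3.4 (Analysis Populations) defines ECYC as "ITT subjects with at least one cycle for which" three conditions hold together: (A) no pregnancy in the cycle, (B) a diary assessment of bleeding, and "C) the cycle has 14 or more days data".

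SAP 3.8.5 (Bleeding and Spotting) computes bleeding or spotting days per woman per cycle, "including the missing value imputation at cycles with less than 28 days but at least 14 days data", "and then summarized by 6-number statistics for ECYC population". Table 14.3.8 in SAP 5.2 is also listed for ECYC.

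The same section ends: "Subjects who discontinue the study due to bleeding complaints prior to completing one 28-day cycle will be included in the bleeding analysis". It sets no minimum number of days. Protocol 20.7 contains the same sentence, but the ECYC definition in protocol 20.1 has no 14-day condition.

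The scaling method is in SAP 3.8.4 (Device Expel and Subject Discomfort): for a partial cycle, "missing value will be imputed by the average in the same cycle for the subject", then rounded to an integer.

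**The concern.** A woman who leaves during her first cycle has only that cycle. With 13 or fewer diary days she fails criterion C and is outside ECYC, yet SAP 3.8.5 says she is in the analysis that is run on ECYC. Two programmers following the text could produce different tables.

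The exclusion is related to the outcome, because these women left on account of the symptom being tabulated. Bleeding and spotting pattern is a named tolerability endpoint (SAP 2.4.2, protocol 5.2). If criterion C governs, Table 14.3.8 describes Cycle 1 bleeding without the women who tolerated it for the shortest time. If the inclusion sentence governs, the table has no defined value for them.

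**Working it through.** **Inputs.** ECYC criterion C (SAP 3.4); inclusion sentence, population and 14-to-27-day scaling range (SAP 3.8.5); scaling method and example (SAP 3.8.4).

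**Step 1: reproduce the SAP's example.** With b event days in d days of data, the scaled count is b + (b/d) × (28 − d), which equals b × 28/d. The SAP's case is "a subject at Cycle 6 has only 20 days data, of which 3 days with" cramping: 3 + (3/20) × 8 = 4.2. The SAP says "which will be 4 after rounding to integer", so its figure is reproduced.

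**Step 2: apply the rules by length of record in the only cycle.**

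| Diary days | Meets criterion C? | Inclusion sentence | Counting rule |
|---|---|---|---|
| 14 to 27 | Yes | Included | Scaled to 28 |
| 13 or fewer | No | Included | None |

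In the first row the provisions agree, and the inclusion sentence adds nothing to criterion C. In the second row it would add something, but criterion C blocks it.

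**Step 3: look for a tie-breaker.** SAP 3.1.3 gives specific sections priority over the general policies of 3.1.3. It does not mention the population definitions in 3.4. Even if 3.8.5 is allowed to prevail, the missing counting rule remains.

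**Step 4: the discontinuity at 14 days.** A woman bleeding on 14 of 14 days is scaled to 14 × 28/14 = 28. A woman bleeding on 13 of 13 days is either absent or has no defined value. Extending the SAP's rule below 14 days would multiply the count by 28/d: 28/13 = 2.15, 28/10 = 2.8, 28/7 = 4. These factors show how much depends on the choice; they do not show that scaling is right.

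**Step 5: illustrative effect on the Cycle 1 mean.** Assumptions, none from the documents except the target of 250 women: k early stoppers, each bleeding on 10 of 10 days, and the others averaging 8 days. The mean is 8.00 if the k women are excluded, ((250 − k) × 8 + 10k)/250 if entered unscaled, and ((250 − k) × 8 + 28k)/250 if scaled.

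| k | Excluded | Unscaled | Scaled |
|---|---|---|---|
| 5 | 8.00 | (1960 + 50)/250 = 8.04 | (1960 + 140)/250 = 8.40 |
| 10 | 8.00 | (1920 + 100)/250 = 8.08 | (1920 + 280)/250 = 8.80 |

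If the others average 10 days, scaled entry instead of exclusion moves the mean by 18k/250: 0.07 day for k = 1 and 0.36 for k = 5. The maximum is more sensitive: each such woman contributes 28, 10 or nothing, depending on the rule.

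**The case against.** **The provisions can be read together.** On this view partial first cycles count, subject to a 14-day minimum. That works for women with 14 to 27 days, and there is no fault for them. It does not settle the shorter records, because the inclusion sentence has no minimum.

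**The women are not lost from the report.** This stands. SAP 3.2 and Table 14.1.2 list early discontinuations with reason and days on study. Tables 14.3.1.6 and 14.3.2.2 cover adverse events leading to discontinuation. SAP 3.8.3 gives safety-related removal rates, and the diary listing 16.2.8.1 is on ITT. Discontinuation and its reasons are also a tolerability endpoint. The gap is confined to Table 14.3.8.

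**A reader might infer that these women enter with a raw, too-low count, so that Cycle 1 is bound to look better than it was.** The documents do not support that. The SAP never says that raw counts below 14 days go into the table. A raw count need not lower the mean: 12 bleeding days in 13 would raise a mean of 10. Calling a raw count too low also assumes that bleeding just after placement would continue at the same rate for 28 days, and a short early window could overstate a full cycle.

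**A reader might also infer that criterion C alone created the problem.** That is only partly so. The protocol restricts ECYC to Evaluable for Pregnancy subjects, who must be aged 18 to 35 and have a diary cycle with intercourse and no backup method, or a pregnancy with the device in place. Some early stoppers could fail that definition too. The SAP widened the base to ITT while adding the 14-day condition.

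**The number may be zero.** This stands. The first scheduled visit after placement is Week 6 ± 2, and no count of removals before Day 14 is given.

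**Conclusion.** The contradiction holds for women who discontinue because of bleeding with fewer than 14 diary days in their only cycle. SAP 3.4 excludes them, SAP 3.8.5 and protocol 20.7 include them, and there is no counting rule if they are included. This is a conflict between two stated rules, with an exclusion tied to the outcome.

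Its consequence is probably modest. The summary is descriptive, the endpoint is secondary, the study is single-arm, and the same women appear in other outputs. Under the assumptions shown, the mean changes by at most 0.4 day with 5 affected women and 0.8 day with 10. The true number is unknown, so the size and direction of any distortion cannot be stated. It should be corrected because the table cannot be reproduced unambiguously from the text and the correction is cheap.

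**What to change.** 1. In SAP 3.4 or 3.8.5, waive criterion C, and only criterion C, for women who leave because of bleeding before finishing one 28-day cycle. Criteria A and B must still apply; a general alternative route into ECYC would admit women with no diary data at all.
2. Report those with fewer than 14 diary days in a separate row of Table 14.3.8. Give their number (including zero) and their observed bleeding and spotting days over observed diary days. Do not scale them to 28 or mix them into the 28-day totals.
3. Limit the exception to the bleeding table, so that the ECYC demographics in Table 14.1.7ECYC do not change.
4. Label it as a clarification made after the Year 1 analysis. SAP 3.1.2 says that analysis has been done and was final for the 1-year data, which include Cycle 1 bleeding. The study report should say which reading was used then.

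The cost is a short SAP addition and one table row. Percentages from short records are variable, and the bleeding summary may look slightly less favourable.
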